10.8. Physical Examination

Data summary will be provided for Physical Examination, including:

- Physical Exam
- Vital Signs
- Vascular Perfusion Assessments
- Multiple DFUs

11. Statistical Methods and Issues

The statistical analysis will be performed by the Clinical Biostatistics Department and/or an approved external vendor.

11.1. Methods of Analysis

11.1.1. Efficacy Endpoints

Confidence interval for proportions:

The method used to compute the two-sided 95% confidence interval (CI) for a single proportion will be the 'exact' method of Clopper and Pearson. For two proportions, the

Confidential Page 19 of 23

two-sided 95% CI for the proportion difference will be calculated based on the Z-test with continuity correction.

11.1.2. Standard calculations

The following calculations will be used:

Equation 1. Age of Ulcer

$$Age = int \left(\frac{(date\ of\ ulcer\ at\ baseline - date\ of\ birth + 1)}{365.25} \right)$$

Equation 2. Clinical Trial Duration for a Subject

For subjects completing the study:

2a) Duration (days) = Final Follow up visit date - Randomization Visit Date

If a subject has not finished treatment (e.g., withdrawals, loss-to-follow-up, etc.)

2b) $Duration_{Withdrawal}(days) = Date \ of \ Withdrawal - Randomization \ Date + 1$

Equation 3. Duration of Adverse Events

 $Duration_{AE} = Onset\ Date_{AE} - Randomization\ Date_{AE} + 1$

Equation 4. Time to Complete Wound Closure

4a) Days to Complete Wound Closure $_{Investigator-based} = (Date\ of\ Last\ Confirmation\ Visit_{EDC}) - (Randomization\ Date) + 1$

Important: This metric will only be calculated for subjects who achieve investigator-based complete wound closure.

EDC: Indicates closure as defined in the EDC system; the investigator-noted closure.

Confidential Page 20 of 23

4b) Days to Complete Wound Closure_{Planimetric} = (Date of Last of Two Successive Readings of $0cm^2_{TA}$) – (Randomization Date) + 1

Important. Planimetric wound closure will only be calculated for subjects who achieve planimetric-based complete wound closure during the Treatment Phase.

TA: Size from imaging vendor (Tissue Analytics, Inc.) database.

Equation 5. Rate of Wound Closure

Rate of Wound Closure (
$$^{\%}$$
 Area/ $_{Week}$) = $\frac{7 \times (Area_{baseline} - Area_{final})}{Area_{baseline} \times Duration}$

Equation 6. Costs Associated with Applied CPT or DRG Codes

- 6a) $CPT\ Total\ Cost_{Study-Wide} = \sum Estimated\ Cost_{All\ Cohorts}$
- 6b) $CPT\ Total\ Cost_{Cohort\ X} = \sum Estimated\ Cost_{Schort\ X}$
- 6c) CPT Average $Cost_{Study-Wide} = \frac{\sum Estimated Costs_{Study-Wide}}{n_{all costs}}$
- 6d) $CPT \ Average \ Cost_{Cohort \ X} = \frac{\sum Estimated \ Costs_{Cohort \ X}}{n_{cohort-based \ costs}}$

Estimated Costs are based on CPT-10 codes.

Equation 7. Costs Associated with Use of Product

- 7a) $Cost \ All \ Product_{Study-Wide} = \sum Costs \ Per \ Product_{All \ Cohorts}$
- 7b) $Cost \ All \ Product_{Cohort \ X} = \sum Costs \ Per \ Product_{Cohort \ X}$

Confidential Page 21 of 23

7c) Average Cost All Product_{Study-Wide} =
$$\frac{\sum Costs \ Per \ Product_{Study-Wide}}{n_{all \ costs}}$$

7d) Average Cost All Product_{Cohort X} =
$$\frac{\sum Costs \ Per \ Product_{Cohort \ X}}{n_{cohort-based \ costs}}$$

7e) Average Cost Per Week_{Study-Wide} =
$$\frac{\left(\frac{\sum Costs \, Per \, Product_{Study-Wide}}{n_{all \, costs}}\right)}{12}$$

7f) Average Cost Per Week_{Cohort X} =
$$\frac{\left(\frac{\sum Costs\ Per\ Product_{Cohort\ X}}{n_{cohort-based\ costs}}\right)}{12}$$

Cost of Product is based on (list price? Cost in study?)

Equation 8. Average Applications Per Patient

8a)
$$Avg. Applications/Subject_{Study-Wide} = \frac{\sum Applications_{Study-Wide}}{n_{all subjects}}$$

8b)
$$Avg.Applications/Subject_{Cohort X} = \frac{\sum Applications_{Cohort X}}{n_{Cohort X}}$$

Equation 9. % ulcer size reduction

9a) $\frac{\text{% ulcer size reduction} =}{\text{Ulcer size at last treatment visit-Ulcer size at randomization visit}}{\text{Ulcer size at randomization}} * 100$

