
Subject Duration:
	
All subjects will have a SOC screening period of up to 2 weeks ± 3 days prior to randomization (Day 0). Investigational product with SOC treatments or SOC alone treatments will begin on Day 0 (randomization) and will be applied weekly for up to 11 weeks ± 3 days. If the wound closes on or before week 11, follow-up will begin and will last 2 weeks ± 3 days after the date of closure. If the wound does not close by week 12, the subject will be immediately exited from the study and no further follow-up will occur as part of the study. The total duration for a single subject may last up to 16 weeks ± 3 days.

Statistical Methods & Analyses:
	
This is a prospective, multicenter, parallel-group, randomized, three-arm trial designed to assess the proportion of subjects achieving complete wound closure of their DFUs, in a population with adequate arterial circulation, following up to 11 weeks of treatment receiving either AMNIOEXCEL Plus Placental Allograft Membrane with SOC, Apligraf bi-layered skin substitute with SOC, or SOC alone. Subjects will be randomized 1:1:1, to receive either

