7 STUDY INTERVENTION DISCONTINUATION AND SUBJECT DISCONTINUATION/WITHDRAWAL

7.1 DISCONTINUATION OF STUDY INTERVENTION

For Subjects Who Develop an Infection:

Subjects who, during the course of the Treatment Phase, develop clinical signs and/or symptoms of infection (e.g., erythema, edema, pain, inflammation, increased drainage etc.) and in the opinion of the Investigator, require oral antibiotic therapy may receive a single course of oral antibiotics during the Treatment Phase of the study. **Should a second consecutive course be required/desired, the subject will be exited from the study.** This antibiotic therapy will be noted on the Concomitant Medications eCRF.

In addition to the above, for those subjects receiving Apligraf or AMNIOEXCEL Plus and develop signs/symptoms of infection, application of those allografts will be withheld on that visit. Application of allografts may be withheld for no more than 1 week at a time and no more than twice (non-consecutive visits) during the 12-week Treatment Phase. If signs and symptoms of infection requiring antibiotic therapy persist for more than one visit, or appear on more than 2 non-consecutive visits during the Treatment Phase, the subject will be discontinued from study participation.

For Subjects Whose Wound Closes:

Discontinuation from treatment in any of the study cohorts does not mean discontinuation from the study. There is one scenario in which a subject may continue in the study after intervention is final:

After treatment with AMNIOEXCEL Plus, Apligraf, and/or SOC **AND** if the subject's wound is documented as closed at or before week 12, the subject will continue to be monitored for two weeks to confirm wound closure. This is noted as week 13 and 14 in the Schedule of Activities, above, but may occur earlier.

If the subject's wound has NOT closed by week 12, the subject will be considered a study failure and will not have any further study visits.

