9.2. Secondary Endpoint Analysis

The secondary endpoints that will be analyzed as part of this trial are as follows:

• Proportion of subjects with complete closure of the study ulcer at or before Week 12 and confirmed 2 weeks later as assessed by computerized planimetry.

Confidential Page 14 of 23

- Proportion of subjects with complete wound closure of the study ulcer at or before Week 12 and confirmed 2 weeks later as assessed by independent, blinded, assessment of photographs.
- The Time to complete wound closure, as assessed by the Investigator.
- The Time to complete wound closure, as assessed by computerized planimetry.
- For those wounds that have closed, the rate of wound closure for each group, as assessed by computerized planimetry.
- Medical resource utilization associated with management of DFU and related complications as determined by a comparison of estimated costs from the presumed billing codes which would have been used for each patient. The summary will be provided by an independent group, results will not be included in this analysis

Proportion of ulcers with complete wound closure during the treatment phase as assessed by planimetry will be compared using Logistic Regression with specified baseline covariates in the model.

Time to complete wound closure will be analyzed using the Log-rank test or Cox Proportional Regression Model. The Kaplan-Meier methods will be used to present the distribution of time to complete wound closure.

Summary statistics will be provided for the rate of wound closure for the two treatment groups.

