11.1.3. Other Variables

Discontinuations

The difference between treatments, both overall and for each primary reason, will be compared by using a 2-sided Fisher's exact test.

Confidential Page 22 of 23

Demographic and Baseline Characteristics

Comparisons between treatment groups of continuous variables will be made by using a one-way analysis of variance with treatment as a factor. For categorical variables, the Fisher's exact test will be used. All tests will be 2-sided and performed at the 0.05 level of significance.

Time-to-Event Data

Time-to-event endpoints including time-to-complete-wound-closure/healed will be evaluated using the Kaplan-Meier method. The log-rank test will be used to compare the distributions between two treatment groups.

Rate of Wound Closure, as Assessed by Computerized planimetry

Analysis of Covariance (ANCOVA) will be used to compare the rate of wound closure for the two treatment groups.

Safety Data

The primary safety endpoint for this study is any severe device-related complication where relationship to the device was assessed by the clinical event committee possible, probably, or definite. Fisher's exact test will be used to compare incidence rates of serious device-related complications as well as for any device-related complication, and for specific complications between the treatment group and the control group.

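### SAP 11.1.2: Eq 9 has a reversed sign, Eqs 1 and 3 do not compute what their titles say, and Eq 5 (rate of wound closure) leaves Duration and the final area undefined

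*SAP*

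**What the plan says.** SAP 11.1.2 opens its list of equations with "The following calculations will be used", so they are operative rules, not illustrations.

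- **Eq 5 (rate of wound closure).** The numerator is 7 times the difference between baseline and final area. The denominator is "Area_{baseline} \times Duration". Neither Duration nor the final area is defined there, and no other equation is cited. The result is labelled percent area per week, but the formula has no factor of 100.
- **Use of Eq 5.** SAP 9.2 lists as a secondary endpoint "For those wounds that have closed, the rate of wound closure for each group, as assessed by computerized planimetry". SAP 11.1.3 adds: "Analysis of Covariance (ANCOVA) will be used to compare the rate of wound closure for the two treatment groups". SAP 9.4 plans the same rate ad hoc for all wounds and for non-healed wounds.
- **Eq 2 (trial duration).** For completers: "2a) Duration (days) = Final Follow up visit date - Randomization Visit Date". Eq 2b, for withdrawals, carries a subscript and adds one day.
- **Eq 4 (time to closure).** Eq 4a ends at the last confirmation visit and Eq 4b at the second of two successive zero readings; each adds one day. The Eq 4b note says: "Planimetric wound closure will only be calculated for subjects who achieve planimetric-based complete wound closure during the Treatment Phase".
- **Follow-up after closure.** For closure by Week 11, the protocol synopsis says "follow-up will begin and will last 2 weeks ± 3 days after the date of closure". Protocol 7.1, for closure at or before Week 12, says "the subject will continue to be monitored for two weeks to confirm wound closure".
- **Eq 9** (titled percent ulcer size reduction) subtracts the randomization size from the last treatment-visit size. **Eq 1** (titled Age of Ulcer) subtracts date of birth from an ulcer date at baseline, in whole years. **Eq 3** (titled Duration of Adverse Events) subtracts the randomization date from the onset date and adds one.

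**The concern.** Three of these formulas do not give what their titles promise, whatever reading is taken. A fourth, for a secondary endpoint, cannot be programmed without a choice that the SAP does not make. The obvious word match for Duration is Eq 2a, which measures time in the trial. For a closed wound that interval includes the confirmation period, when there is no area left to close. A programmer who took Eq 4b instead would report a different secondary-endpoint value from the same data. For wounds still open at Week 12, Eq 2a has no clear end date. Those subjects have no follow-up-phase visit, and protocol 6.1.2.1 also calls the weekly treatment visits follow-up visits. Yet SAP 9.4 needs a rate for them.

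**Working it through.** The documents report no numerical result from these equations, so there is no stated figure to reproduce. Each formula is evaluated directly.

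**Eq 9**, (last - randomization) / randomization x 100, with illustrative areas:
- 4 cm² to 0: (0 - 4)/4 x 100 = -100%.
- 4 cm² to 1 cm²: (1 - 4)/4 x 100 = -75%.
- 4 cm² to 5 cm²: (5 - 4)/4 x 100 = +25%, so growth appears as a positive reduction.

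**Eq 1**, with an illustrative subject born 1 January 1960, a baseline date of 1 December 2018 and an ulcer 91 days old. The formula returns 58, the subject's age. Putting the ulcer onset date in its place also returns 58. Eligible ulcers are 4 weeks to 12 months old and subjects are at least 21 (protocol 5.1), so the result cannot be an ulcer age.

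**Eq 3**, with onset 30 days after randomization and a 5-day event: 30 + 1 = 31, the study day of onset. Resolution - onset + 1 gives 5.

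**Eq 5**, closed wound. With a final area of 0 the baseline area cancels, and after multiplying by 100 the rate is 700/Duration. Let T be days from randomization to first observed closure (28, 56 and 84 at Weeks 4, 8 and 12). Assumptions: planimetric area is 0 at closure and afterwards, visits fall on nominal days, and for Eq 4b the second zero comes one week after the first.

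| Duration taken as | Week 4 | Week 8 | Week 12 |
|---|---|---|---|
| First observed closure (T) | 700/28 = 25.0 | 700/56 = 12.5 | 700/84 = 8.33 |
| Eq 2a (T + 14) | 700/42 = 16.7 | 700/70 = 10.0 | 700/98 = 7.14 |
| Eq 4a read literally (T + 15) | 700/43 = 16.3 | 700/71 = 9.9 | 700/99 = 7.07 |
| Eq 4b (T + 8) | 700/36 = 19.4 | 700/64 = 10.9 | not claimed |

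Eq 2a is below the first-closure value by 14/42 = 33%, 14/70 = 20% and 14/98 = 14%. With the final visit 11 to 17 days after closure (2 weeks ± 3 days), Eq 2a gives 700/45 = 15.6 to 700/39 = 17.9 at Week 4 and 700/73 = 9.6 to 700/67 = 10.4 at Week 8. The synopsis window covers closure by Week 11 only. For a Week 12 closure, Table 2 puts the final visit at day 98 ± 3, which gives 700/101 = 6.93 to 700/95 = 7.37.

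No Week 12 value is given for Eq 4b. The second zero would then fall in follow-up, and the Eq 4b note limits the calculation to closure during the Treatment Phase.

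**The case against.** The strongest reply is that the Eq 5 losses depend on two choices the SAP does not make.

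- **The reading.** Eq 2 is titled as trial duration and nothing links it to Eq 5. Since Eq 5 pairs a baseline area with a final area, the interval between those two measurements is at least as natural. This stands: the certain defect is that the term is undefined.
- **The benchmark.** The SAP never says the rate runs to first observed closure. Both its time-to-closure equations, read literally, end at confirmation. Against Eq 4a, Eq 2a is one day shorter and gives a rate about 2% higher (43/42 = 1.024). This stands too, so a reader who infers that the SAP will understate the closure rate by a third goes further than the documents allow.
- **The gap.** The 14 days applies to confirmed closures. A wound open at follow-up visit 1 exits after about 7 days. Windows anchored to Day 0 allow a Week 12 to Week 14 gap of 8 to 20 days. Follow-up is triggered by the investigator's closure, while Eq 5 uses planimetry.

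A reader might also infer that the ANCOVA comparison between arms is biased. On the Eq 2a scale the difference between a Week 4 and a Week 8 closer does fall, from 25.0 - 12.5 = 12.5 to 16.67 - 10.00 = 6.67. But the spread shrinks as well and any one definition applies to every arm, so the documents do not show bias in the test.

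Finally, the stakes are limited. Protocol 9.4.6 calls the secondary analyses exploratory, and protocol 9.2 says the study is not adequate for hypothesis testing. None of this rescues Eqs 1, 3 and 9, which fail on any reading.

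**Conclusion.** The point holds in two parts of different strength.

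**Certain.** Eq 9 has the right magnitude and the wrong sign. Eq 1 returns subject age. Eq 3 returns onset day. Eq 5 has an undefined Duration, an undefined final area and no factor of 100.

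**Conditional.** If Duration is read as Eq 2a and compared with first observed closure, the rate for a confirmed closure is lower by 33%, 20% and 14% at Weeks 4, 8 and 12, with the largest loss for the fastest closers. Other readings available within the SAP give other values: at Week 4 they run from 16.3 to 25.0 %/week for the same wound. That spread is the practical problem, because the SAP does not say which value will be reported.

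The primary endpoint does not use these equations. Eq 9 feeds an ad hoc table only, and no planned output is shown to depend on Eq 1 or Eq 3. This should be corrected, but it does not threaten the trial's main result.

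**What to change.** - **Eq 9:** (randomization size - last treatment-visit size) / randomization size x 100.
- **Eq 1:** retitle as subject age; for ulcer age use the recorded ulcer duration, already a listed covariate.
- **Eq 3:** resolution date (or study exit if ongoing) - onset date + 1, or delete it.
- **Eq 5:** define Duration as days from randomization to the planimetry visit that supplies the final area. Multiply by 100 and use one day-count convention for all subjects; Eqs 2a and 2b now differ by a day.
- **Final area, confirmed planimetric closers:** the first zero that is confirmed at the next reading, which may be a follow-up visit.
- **Final area, all others:** the last available planimetry, including follow-up. Stopping at the last Treatment-Phase reading would score a wound at zero at Week 8 but open at follow-up visit 1 as 100% closed, within the non-healed group.
- **Eqs 4a and 4b:** state whether they end at first or confirmed closure, so that time and rate share the same end date.

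The cost is SAP text and programming. Visit dates, planimetry images, ulcer duration and adverse event onset and resolution dates are already collected under protocol Table 2 and section 8.2.

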1 PROTOCOL SUMMARY

Table 1: Protocol Synopsis

Title:	A Prospective, Multi-Center, Randomized, Parallel-group Study Comparing AMNIOEXCEL Plus Placental Allograft Membrane to Apligraf Bi-layered Skin Substitute and Standard of Care Procedures in the Management of Diabetic Foot Ulcers
Short Title:	AMNIOEXCEL Plus vs Apligraf vs Standard of Care (SOC) in the Management of Diabetic Foot Ulcers
Study Description:	This is a multicenter, randomized, parallel-group study comparing the outcomes associated with the use of AMNIOEXCEL Plus Placental Allograft Membrane, Apligraf bi-layered skin substitute and SOC alone in the management of diabetic foot ulcers (DFUs).
Pre/Post-Market:	Post-Market
Study Design:	This study will have three (3) phases: (1) a Screening Phase, (2) a Treatment Phase, and (3) a Follow-up Phase. Subjects will be seen weekly in the Screening and Treatment Phases. Subjects who achieve wound closure during the Treatment Phase will be entered into the Follow-up Phase and will return to the site for up two (2) additional weeks for confirmation visits. An interim analysis will occur after 50% of subjects have reached the primary endpoint.
Primary Objective:	The primary objective of this study is to compare outcomes associated with the use of AMNIOEXCEL Plus Placental Allograft Membrane, Apligraf living, bi-layered skin substitute and SOC in the management of DFUs.
Secondary Objective(s):	The secondary objectives of this study are to: 
 1. Determine the proportion of subjects in each study arm with complete closure of the study ulcer at or before 12 weeks of treatment 2. Determine the time to complete wound closure in each study arm 3. Determine the rate of wound closure in each study arm 4. Assess medical resource utilization outcomes in each study arm
Safety Objective:	The safety objective of this study is to assess adverse events associated with any of the investigational products and/or study procedures in the management of DFUs.
Exploratory Objective(s):	The exploratory objectives of this study are to: 
 1. Determine the proportion of subjects in each cohort whose wounds are closed at 4 weeks of treatment. 2. Determine the effect of any covariate on the primary endpoint.

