8.1.5 WEEK 12 (84 ± 3 DAYS)

1. Review Study Compliance with the Subject (Treatment Compliance Review)
2. Collect MRU Data for the Previous Week (MRU Assessment)
3. Collect Images of the DFU (Photography)
4. Perform Ulcer Assessments
5. Apply Boot, if applicable
6. Document Adverse Events
7. Document Concomitant Medications & Procedures (ConMeds and Other Procedures)

8.1.6 FOLLOW-UP VISITS - WEEKS 13 & 14 (91 & 98 ± 3 DAYS)

1. Collect MRU Data for the Previous Week (MRU Assessment)
2. Collect Images of the DFU (Photography)
3. Perform Ulcer Assessments
4. Apply Boot, if applicable
5. Document Adverse Events

6. Document Concomitant Medications & Procedures (ConMeds and Other Procedures)

IMPORTANT: If the subject’s wound is open at Follow-up visit 1 (e.g., week 13), the subject is exited from the study and is marked as having completed their study requirements. The site will note why they believe the wound is still open.

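### SAP Equation 4a dates closure about 14 days late and no censoring time is stated: reported closure times run late, and the Kaplan-Meier tail depends on an unwritten choice

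*SAP*

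**What the plan says.** **Event date.** SAP 11.1.2, Equation 4a, counts days from randomization to "Date\ of\ Last\ Confirmation\ Visit_{EDC", plus 1. A footnote explains the subscript as closure recorded by the investigator in the EDC system. Equation 4b counts to the "Date of Last of Two Successive Readings of" 0 cm². Each has a note. For 4a: "This metric will only be calculated for subjects who achieve investigator-based complete wound closure". For 4b: "Planimetric wound closure will only be calculated for subjects who achieve planimetric-based complete wound closure during the Treatment Phase".

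**Confirmation visits.** Under Study Design, the protocol synopsis says that subjects who close "will return to the site for up two (2) additional weeks for confirmation visits". Under Subject Duration it says "follow-up will begin and will last 2 weeks ± 3 days after the date of closure". SAP 9.1 requires closure at both follow-up visits for success.

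**Who leaves when.** For a wound still open at Week 12, Protocol 7.1 says "the subject will be considered a study failure and will not have any further study visits". Protocol 8.1.6 covers reopening: if the "wound is open at Follow-up visit 1 (e.g., week 13), the subject is exited from the study".

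**Analysis.** SAP 9.2 and 11.1.3 plan Kaplan-Meier curves with a log-rank test or Cox model, and SAP 8.1 and 9 put secondary endpoints on the ITT population. Protocol 9.4.6 promises a Kaplan-Meier median; SAP 9.2 promises only the distribution. SAP 9.5 calls subjects who discontinue before closure failures but assigns them no time. Neither document states a censoring time. The protocol synopsis (secondary endpoint 4) limits the planimetric time to wounds that closed; Protocol Table 3, Protocol 9.1 and SAP 9.2 do not.

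**The concern.** Two of the six secondary endpoints are times to closure. In 4a the event is placed after a two-week confirmation period that only closers go through, while unhealed subjects leave at Week 12. Unless censoring is moved by the same two weeks, late events occur when the unhealed have already left the risk set. A Kaplan-Meier curve then attributes near-complete closure to an arm in which most wounds may never have closed, and reports a median that does not exist. Even with matching censoring, a reader would take the reported times as times to closure when they are about two weeks (4a) or one week (4b) longer.

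**Working it through.** **Inputs.** Week 12 is day 84 ± 3 and the follow-up visits after a Week 12 closure are days 91 and 98 ± 3 (Protocol 8.1.5, 8.1.6). There are 38 subjects per arm and an assumed maximum closure rate of 90% (SAP 5). Visits are taken as weekly and on schedule. Closure counts, timing and reopening below are assumptions for illustration.

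**1. Lag.** The plan's own figure reproduces: 98 − 84 = 14 days, or 11 to 17 days with the ± 3 day window. For closure first seen at week w, with the SAP's +1:

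- first noted: 7w + 1
- Equation 4b: 7(w + 1) + 1 = 7w + 8
- Equation 4a: 7(w + 2) + 1 = 7w + 15
- exit of a non-closer at Week 12: 7 × 12 + 1 = 85

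| Closure first seen | First noted | 4b | 4a |
|---|---|---|---|
| Week 10 | 71 | 78 | 85 |
| Week 11 | 78 | 85 | 92 |
| Week 12 | 85 | 92 | 99 |

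**2. Equation 4a, non-closers censored at exit (day 85).** Assume 12 of 38 close, one per week, and 26 never close.

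- Day 85: 10 events, still open 28/38 = 0.737, so 26.3% closed. The 26 non-closers then leave and 2 subjects remain.
- Day 92: 0.737 × 1/2 = 0.368, so 63.2% closed. The median is day 92.
- Day 99: 0.368 × 0/1 = 0, so 100% closed.

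Dated at first noted closure, the same data end at 12/38 = 31.6% with the median not reached.

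**3. Variations.** Suppose one of the 26 non-closers instead closed at Week 12, reopened at follow-up visit 2 and stayed at risk to day 99. The factors become 2/3 and 1/2: 0.737 × 2/3 × 1/2 = 0.246, and the curve ends at 75.4%. With 24 of 38 closing, two per week: 20/38 = 52.6% at day 85; 18/38 × 2/4 = 0.237, so 76.3% at day 92; 100% at day 99. The correct figure is 63.2%. With one such reopener, 18/38 × 3/5 × 1/3 = 0.095, so 90.5%.

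Simulated arms of 38, four assumed timing patterns, 10–20% of first closures reopening: the mean end of the curve is 83–97% when 30% truly close and 94–98% when 60% do. At the plan's 90%, with 5% reopening, it is 98–100%.

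**4. Equation 4a, non-closers carried to day 99.** Every event precedes or coincides with censoring, so the example in step 2 ends at 31.6%. Only the times move, by 14 days. With constant weekly hazard, 27 of 38 closing gives a median of 64 instead of 50 days, and 34 of 38 gives 43 instead of 29.

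**5. Equation 4b.** A Week 11 first reading is confirmed on day 85, so only Week 12 first readings can fall later. In the step 2 example 11/38 = 28.9% are closed by day 85. If a second zero at Week 13 counts, one subject remains at risk and the curve jumps to 100% on day 92. If both readings must fall by Week 12, there is no later event and no tail effect; the Week 12 closure is then not counted.

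**6. Closers only.** With non-closers left out, the step 2 arm has 12 subjects and 12 events, so the curve ends at 12/12 = 100%. The same holds in every arm whatever the closure rate.

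**7. Log-rank test.** 3,000 simulated trials, 38 per arm, constant weekly hazard. Rejection with the first-noted date against 4a with exit censoring: 5.8% and 5.3% with 50% closing in both arms; 76.9% and 69.9% at 35% against 65%; 45.4% and 39.1% at 30% against 50%. Under 4a with censoring at day 99 the results equal those for the first-noted date.

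**The case against.** The endpoint is confirmed closure, so dating it at confirmation is a legitimate convention. With matching censoring the comparison is sound, and no planned analysis sets 4a against 4b. That stands as far as it goes, but the equation is labelled days to complete wound closure, and no matching censoring date is given.

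The EDC footnote could be taken to mean the date on which the investigator first noted closure. It explains the subscript, whereas the equation names the last confirmation visit. If first-noted closure was intended, the equation needs correcting.

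Stronger readings are tempting, and the documents do not support them:

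- *The planned curve will reach 100%.* This needs censoring at Week 12 exit, which the plan nowhere states, and at least one confirmed closure first seen after Week 10. At the plan's only closure figure (90%) the distortion is from 90% to 98–100%.
- *Equation 4b has the same fault.* Only if a Week 12 zero may be confirmed at Week 13. The note's limit to the Treatment Phase leaves that unclear.
- *Kaplan-Meier is planned on closers only.* The notes under Equation 4 and synopsis endpoint 4 lean that way, the latter for planimetry; SAP 8.1 and 9 say ITT. The documents conflict, and neither reading can be taken as settled.
- *Every report will carry a wrong median.* Only the protocol promises a median.

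The synopsis also starts follow-up for closures up to Week 11, where Protocol 7.1 says Week 12. With Week 11 as the limit, the latest 4a time is day 92, still after exit.

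**Conclusion.** The point holds, at moderate weight. As written, 4a times are about 14 days long (11 to 17 with the visit window) and 4b times nominally 7 days long. That follows from the text and needs no assumption beyond weekly visits for 4b. The distortion of the curve is conditional on Week 12-exit censoring. Under that rule it can be large at low closure rates (100% against 31.6% in the illustration) and is small near 90%. Late reopeners reduce it but do not remove it.

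A reader might infer that the trial's main result is at risk. It is not: the primary endpoint and closure proportions do not use Equation 4, and type I error was 4.3–6.0% under all rules tested. Protocol 9.4.6 labels these analyses exploratory, and SAP 5 says the study is not powered for testing. The harm is misleading times, curves and medians, plus some loss of log-rank power if exit censoring is used.

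**What to change.** 1. In 4a, date the event at the first visit at which the later-confirmed closure was noted. In 4b, use the first of the two successive zero readings.
2. State that the notes under Equation 4 define event times only, and that Kaplan-Meier, log-rank and Cox include all ITT subjects. Amend synopsis endpoint 4 to match.
3. Censor unhealed and reopened subjects at the end of the Week 12 window (84 + 3 + 1 = day 88), so that Week 12 closures count first. In simulation this recovers 30.1%, 59.9% and 90.1% for true 30%, 60% and 90%. Censoring each non-closer at their own Week 12 visit date instead gives 33–38% at true 30% and 64–72% at true 60%.
4. Carry subjects who discontinue before closure as failures to Week 12, in line with SAP 9.5, with censoring at last assessment as a sensitivity analysis. The choice matters: with 20% dropout the plateau is 26–28% against 30%, or 52–55% against 60%.
5. State how undetermined subjects (closed, but a follow-up visit missed; SAP 9.1) are dated and classified.

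Alternatively, label the endpoint time to confirmed closure, use one confirmation convention in 4a and 4b, and censor non-closers no earlier than the last possible confirmation visit.

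The cost is a few sentences of SAP text, one synopsis line and derivation code; visit dates and planimetry readings are already collected. One limit remains: Week 1 imaging is optional in the Apligraf arm (Protocol 8.1.4), so its first planimetric reading after treatment starts may be at Week 2.
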